### **8.5.3 Analysis of safety outcomes**

The number and percentage of patients diagnosed with AI will be tabulated as follows:

- Patients with complete AI

In addition, the number and percentage of patients diagnosed with AI will be tabulated according to the way of diagnosis. The association between AI diagnosis and OCS down-titration will be explored.

Spaghetti plots may be produced for patients with Partial AI throughout the OCS reduction phase, showing cortisol levels over time.

The incidence of AEs and SAEs will be summarized overall and stratified by relationship to study intervention and severity grade.

The annualized rate of asthma exacerbations will be summarized using mean, 95% CI, and dispersion based on the negative binomial distribution.

Glucocorticoid toxicity index will be summarized over time. Statistical correlation between GTI and daily OCS dose will be explored.

The number and percentage of patients diagnosed with AI will be tabulated overall and by baseline OCS dose according to the way of diagnosis: morning cortisol or ACTH stimulation test, morning cortisol test, intermediate morning cortisol and ACTH stimulation test, and intermediate morning cortisol and intermediate ACTH stimulation test.

In addition, the number and percentage of patients diagnosed with AI will be tabulated by subgroup according to duration of chronic OCS treatment.

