3.3 Safety variables

Safety variables include:

- Disposition of adrenal function by morning cortisol and/or ACTH test
- Annualised asthma exacerbation rate and number (and percent) of patients with 0, 1, 2, etc exacerbations.
- Annualised asthma exacerbation rate leading to hospitalization or emergency room visit and number (and percent) of patients with 0,1, 2, etc exacerbations leading to hospitalization or emergency room visit
- AEs and SAEs
- Laboratory parameters
- Vital signs

- GTI

Safety analyses will use all available data, including data from unscheduled visits and repeated measurements.

[figure not shown]
Change from baseline to each post-treatment time point where scheduled assessments were made will be calculated for relevant measurements. Adverse events will be summarised by means of descriptive statistics and qualitative summaries.

No safety data will be imputed. The handling of partial/missing dates is detailed in Appendix 8.1.

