3.3.2 Annualised asthma exacerbation rate

The number of asthma exacerbations and the annualised asthma exacerbation rate will be derived and summarized for the on-study period to end of OCS reduction phase at DBL1, on-study period during maintenance phase, and the overall on-study period at DBL2. On-study period to end of OCS reduction phase is defined as from the day of the first dose of study treatment to the end of OCS reduction phase; on-study period during maintenance phase is defined as from the start of the maintenance phase to the scheduled follow-up visit of the main study; and the overall on-study period is defined as from the day of the first dose of study treatment to the scheduled follow-up visit of the main study. A patient will be considered as having an asthma exacerbation if he/she starts a course of SCS (oral, parenteral) due to asthma, or has an emergency room/urgent care visit or a hospitalisation due to asthma.

The annualised asthma exacerbation rate will be calculated using the time-based approach. Annual asthma exacerbation rate = $365.25 \times \text{total number of exacerbations} / \text{total duration of follow-up (days)}$.

The number and annualised rate of exacerbations requiring hospitalisation or an emergency room visit will also be derived and summarised for the on-study period to end of OCS reduction phase at DBL1, on-study period during maintenance phase, and the overall on-study period at DBL2.

As a sensitivity analysis, annualised exacerbation rates will also be calculated using total duration of follow-up less days with exacerbations (+ 7 days per exacerbation) as the denominator.

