Continuous variables will be summarised using the mean, two-sided 95% CI of the mean, the standard deviation, median, minimum value, and maximum value. Categorical variables will be summarised using frequency counts and percentages, as well as a two-sided 95% CI for proportions computed using the exact Clopper-Pearson method. All patients in the corresponding analysis set will be considered the denominator. Time to event data will be summarised using median and 25th and 75th percentiles with 95% CIs. Data will be listed in patient level data listings.

No formal hypothesis will be tested in this study, and no multiplicity adjustment will be applied in the statistical analysis. No imputation will be performed beyond the approach defined for outcome measures in Section 4.2.6.3.

Due to the single-arm study design, external data sources may be used to contextualize any change seen in asthma control, asthma exacerbation rate, or other safety endpoints in patients treated with benralizumab following reduction of OCS. Any data sources identified, together with planned analyses, will be described in a separate analysis plan.

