4.2.7.4 Asthma exacerbations

The number of asthma exacerbations, number of patients with at least one exacerbation, number of exacerbations per patient, duration of exacerbation, number of exacerbations requiring hospitalization, number of exacerbations requiring emergency room visits, and number of exacerbations requiring OCS/Systemic Corticosteroid use will be summarised for the three study periods as defined in section 3.3.2. All asthma exacerbations will be listed by patient.

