6. CHANGES OF ANALYSIS FROM PROTOCOL

- 1) A sensitivity analysis of the primary outcome has been included in section 4.2.5.2 which excludes any patients with an Important Protocol Deviation related to efficacy. This sensitivity analysis is not specified in the protocol.
- 2) A sensitivity analysis of the first key supportive analysis has been included in section 4.2.5.2 which will require patients with a baseline daily OCS dose of 5mg to achieve a final daily OCS dose of < 5 mg, unless the reason for no further reduction is complete AI. This sensitivity analysis was not included in the protocol.
- 3) In protocol Section 8.5.2.2, a mixed model for repeated measures was planned to analyse the change from baseline in ACQ-6 score. Because phase and study duration will be different between patients, an ANCOVA model will be used to analyse the change from baseline at visit 3, initial morning cortisol test, end of OCS reduction phase and end of maintenance phase, only.

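### The SAP drops the protocol's negative binomial 95% CI and dispersion for the annualised exacerbation rate and does not declare the change

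*SAP*

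**What the plan says.** Protocol 8.5.3 states the method: "The annualized rate of asthma exacerbations will be summarized using mean, 95% CI, and dispersion based on the negative binomial distribution".

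SAP 3.3.2 states another: "The annualised asthma exacerbation rate will be calculated using the time-based approach". The formula is 365.25 times total exacerbations divided by total follow-up days. A sensitivity version shortens the denominator by the days in exacerbation plus 7 days for each one. Both are ratios of totals.

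SAP 3.3 lists the safety variable as "Annualised asthma exacerbation rate and number (and percent) of patients with 0, 1, 2, etc exacerbations". SAP 4.2.7.4, the methods section, does not mention the rate. It lists numbers of exacerbations, of patients affected, of exacerbations per patient and by type of care, together with duration, all of which "will be summarised for the three study periods as defined in section 3.3.2".

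SAP 4.1 supplies the general rules: "Continuous variables will be summarised using the mean, two-sided 95% CI of the mean" for continuous data, and counts and percentages for categorical data "as well as a two-sided 95% CI for proportions computed using the exact Clopper-Pearson method". Time-to-event data have their own rule; event rates have none.

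SAP Section 6 declares three changes from the protocol. Two are added sensitivity analyses. The third concerns ACQ-6, where "a mixed model for repeated measures was planned to analyse the change from baseline in ACQ-6 score" and was replaced by ANCOVA, with a reason given. The exacerbation rate is not among them.

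On the definition, SAP 3.3.2 counts a patient as having an exacerbation if he or she "starts a course of SCS (oral, parenteral) due to asthma, or has an emergency room/urgent care visit or a hospitalisation due to asthma". Protocol 5.2.2 is more detailed.

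**The concern.** The annualised exacerbation rate is one of two key outcome measures for the objective of assessing how the taper affects exacerbations. The study has a single arm, and both documents allow external data to be used to put the rate in context. A rate reported without an interval is hard to use that way, because the reader cannot tell how far it might move by chance. Exacerbation counts are commonly more variable between patients than a Poisson model allows. The dispersion parameter shows how much more, and the negative binomial interval takes it into account.

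There is also a question of process. Section 6 is where the SAP records departures from the protocol. It does so for ACQ-6 but not here, so the reader of the report would not learn that a prespecified summary had been left out.

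**Working it through.** **Step 1. Does any SAP provision supply the protocol's summary?**

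- SAP 3.3.2, main and sensitivity rates: point values only.
- SAP 3.3, patients with 0, 1, 2, etc exacerbations: under SAP 4.1 these percentages get Clopper-Pearson intervals, which are intervals for proportions of patients and not for the annualised rate.
- SAP 4.2.7.4, exacerbations per patient: if treated as continuous, SAP 4.1 gives a mean, 95% CI and SD. That is a mean count over unequal follow-up, not a rate per year.
- SAP 4.1: nothing for a ratio of totals.
- The terms negative binomial and dispersion do not occur in the SAP. Neither Section 6 nor the amendment history records their removal.

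So the interval and dispersion required by protocol 8.5.3 are not planned anywhere in the SAP.

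**Step 2. Is the point estimate affected?**

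The pooled rate and an intercept-only negative binomial rate with a follow-up offset were compared on 100 simulated data sets of 600 patients. Assumed inputs were a rate of 0.7 per year, dispersion 1 and 10% early leavers. When the rate was unrelated to follow-up, the averages were 0.70 and 0.70. When early leavers had three times the rate, they were 0.75 and 0.76. The estimate barely moves.

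**Step 3. How wide is the missing interval?**

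The documents state no expected exacerbation rate, dispersion or precision target, so there is no figure of theirs to reproduce and this is an illustration.

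Inputs:
- n = 600 (protocol 8.2).
- 48 weeks, the upper planned duration in the protocol synopsis, which applies to patients with no exacerbation and no indicated AI risk.
- Rate r = 0.6 per year and dispersion k = 0, 1, 2: assumptions. Every patient is given the same follow-up.

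Formulas: T = weeks x 7 / 365.25; mu = r x T; SE(log rate) = sqrt((1/mu + k) / n); 95% CI = r x exp(+/-1.96 x SE).

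T = 48 x 7 / 365.25 = 0.920 years; mu = 0.6 x 0.920 = 0.552; 1/mu = 1.812.

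| k | SE(log rate) | 95% CI |
|---|---|---|
| 0 | sqrt(1.812/600) = 0.0550 | 0.539-0.668 |
| 1 | sqrt(2.812/600) = 0.0685 | 0.525-0.686 |
| 2 | sqrt(3.812/600) = 0.0797 | 0.513-0.701 |

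A simulation of 4000 trials at k = 1 gave 1.96 x SD of the estimated rate = 0.080. The formula gives 1.96 x 0.6 x 0.0685 = 0.081.

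**Step 4. The shorter period.**

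SAP 3.3.2 also reports the rate from first dose to the end of OCS reduction. Under protocol Table 2 and 5.1.2.1, a patient starting at 5 mg without AI could finish reduction near week 12: 4 weeks of induction, reductions at weeks 4 and 8, then 4 stable weeks. Taking 12 weeks for everyone as a short extreme, T = 0.230 and mu = 0.6 x 0.230 = 0.138. The CI is 0.484-0.744 at k = 0 (SE 0.1099) and 0.470-0.765 at k = 2 (SE 0.1241). At a rate of 1.0 and k = 2, the half-width is 1.96 x 1.0 x 0.1029 = 0.20 per year.

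**Step 5. The definition, side by side.**

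| Element | Protocol 5.2.2 | SAP 3.3.2 |
|---|---|---|
| Steroid course | More than one level above the current titration step, at least 3 consecutive days (one depot injection is equivalent) | Any systemic course started for asthma |
| ER or urgent care | Systemic corticosteroids required | Any visit for asthma |
| Repeat within 7 days of last steroid dose | Same event | Not stated |

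The 7 days per exacerbation in the SAP's sensitivity rate reduce a denominator; they do not merge events.

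**The case against.** The strongest reply is that the SAP omits the model without withdrawing it. Section 3.3.2 derives a variable, the study is descriptive with no hypothesis test, no decision depends on the interval, and the point estimate hardly changes. All of that is true, and it limits the severity. It does not answer the point, because the protocol's summary is itself descriptive and the SAP as written will not produce it.

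Several stronger readings are tempting, and the documents do not support them.

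- A reader might infer that the SAP gives no uncertainty or between-patient variation for exacerbations at all. It does give some: the 0, 1, 2 distribution shows variation between patients, and SAP 4.1 puts intervals on those percentages. Even the annualised rate would get a mean and 95% CI under SAP 4.1 if the formula were read per patient, though still no negative binomial estimate or dispersion.
- A reader might infer that the SAP will count different events from those the protocol intends. That is not shown. Protocol 5.2.2 has the investigator justify each exacerbation and record it in the eCRF, and SAP 3.2.1 uses a therapy reason tied to exacerbations per protocol. If only those records are counted, the wording has no effect. SAP 3.3.2 does not say so.
- A reader might infer that the comparison of substudy and main-study rates planned in protocol Appendix K is compromised, since the substudy uses the negative binomial. The substudy has its own SAP, which is not among the documents and may specify how the main-study rate is obtained.

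**Conclusion.** The point holds as an undeclared omission. Protocol 8.5.3 promises an interval and a dispersion for a key safety rate; the SAP plans neither for that rate, and Section 6 does not say so. It should be fixed, but it does not bias the estimate.

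At 600 patients, 0.6 events per year and 48 weeks, the missing interval runs from about 0.54-0.67 to 0.51-0.70 per year as dispersion goes from 0 to 2. For the period to the end of OCS reduction it would be wider, about 0.48-0.74 to 0.47-0.77 if that period lasted only 12 weeks for everyone. The rate, the dispersion and the equal follow-up are assumptions.

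The definition wording is secondary. The texts differ, but the effect on counts is unknown and may be zero, so no size is given.

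**What to change.** 1. In SAP 4.2.7.4, add an intercept-only negative binomial model for the annualised exacerbation rate with log follow-up time as offset, reporting the rate, 95% CI and dispersion. Keep the pooled rate as a descriptive line.
2. If the departure is to be kept instead, declare and justify it in SAP Section 6, as was done for ACQ-6.
3. In SAP 3.3.2, replace the definition sentence with a cross-reference to protocol 5.2.2, including its 7-day same-event rule, and state that investigator-recorded eCRF exacerbations are what is counted.

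The cost is one standard model on data already collected and one cross-reference, or a single Section 6 entry in place of the model.

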3.3.3 Adverse events

Adverse events (AEs) experienced by the patients will be collected throughout the entire study and will be coded using the latest version of the Medical Dictionary for Regulatory Activities (MedDRA) per the Data Management Plan.

Adverse events will be summarised for on-study period to end of OCS reduction phase at DBL1 and the overall on-study period at DBL2. AEs in the on-study period to end of OCS reduction phase are defined as those with onset between day of the first dose of study treatment and the end of OCS reduction phase, inclusive. AEs in the overall on-study period are defined as those with onset between day of the first dose of study treatment and the

follow-up visit of the main study, inclusive. If follow-up is not available, then use the date of Disposition event of End of Study.

3.3.4 Laboratory variables

Laboratory safety assessments will be performed in a central laboratory at the times detailed in the CSP. The parameters outlined in Section 5.2.4, Table 4 of the CSP will be collected. Laboratory data are to be reported in SI units, except for the blood eosinophils counts which will be reported in conventional units.

Changes in haematology and clinical chemistry variables between baseline and each subsequent assessment will be calculated. For values recorded with a leading greater than or less than ('>', '<') symbol, the reported numeric value will be used for analysis and the value with the symbol will be included in the listings, unless otherwise specified. For example, a value of <0.01 will be analysed as 0.01 and listed as <0.01.

Absolute values will be compared to the relevant reference range and classified as low (below range), normal (within range or on limits) or high (above range). The central laboratory ranges will be used for laboratory variables. All absolute values falling outside the reference ranges will be flagged.

For the purposes of haematology and clinical chemistry shift tables, baseline will be defined as the latest non-missing assessment prior to first IP dose date, and maximum or minimum value post-baseline will be calculated over the entire post-baseline period, including the unscheduled assessments.

For the liver function tests: aspartate aminotransferase (AST), alanine aminotransferase (ALT), alkaline phosphatase, and total bilirubin (TBL), the multiple of the central laboratory upper limit of the normal (ULN) range will be calculated for each data point.

$$\text{Multiple} = \text{Value} / \text{ULN}$$

For example, if the ALT value was 72 IU/L (ULN 36) then the multiple would be 2.

Patients who meet any of the following criteria at any point during the study will be flagged:

- AST $\geq 3 \times \text{ULN}$
- ALT $\geq 3 \times \text{ULN}$
- TBL $\geq 2 \times \text{ULN}$

3.3.5 Vital signs

Pre-dose vital signs (pulse, blood pressure (BP), respiration rate, and body temperature) will be obtained in accordance with schedule provided in the CSP.

Changes in vital signs variables between baseline and each subsequent scheduled assessment will be calculated. Absolute values will be compared to the relevant reference ranges and classified as low (below range), normal (within range or on limits) or high (above range). All values (absolute and change) falling outside the reference ranges (see [Table 3](#)) will be flagged.

Table 3 Vital signs reference ranges

Parameter	Standard Units	Lower Limit	Upper Limit
Diastolic Blood Pressure (DBP)	mmHg	60	120
Systolic Blood Pressure (SBP)	mmHg	100	160
Pulse Rate	Beats/min	40	120
Respiratory Rate	Breaths/min	8	28
Body Temperature	Celsius	36.5	38
Weight	kg	40	200

Body mass index (BMI) will be calculated from the height and weight as follows:

$$BMI (kg/m^2) = weight (kg)/(height (m))^2$$

3.3.6 Glucocorticoid toxicity index

Glucocorticoid toxicity index will be assessed as described by [Miloslavsky et al 2017](#) at the times detailed in the CSP. Only a subset of items from the composite GTI will be assessed in this study: BMI, glucose tolerance (glycosylated haemoglobin), BP, low density lipoprotein, steroid myopathy, skin toxicity, neuropsychiatric toxicity, and infection (items from the Specific List will not be assessed). Full details on GTI composite scoring are given in Appendix H to the CSP.

3.3.7 Physical examination

Complete and brief physical examinations will be performed at timepoints specified in Table 1 of the CSP.

Baseline data will be collected at Visit 1. Any new finding(s) or aggravated existing finding(s), judged as clinically significant by the Investigator, will be reported as an AE as described in Section 6 of the CSP.

3.4 Exploratory variables

3.4.1 Genomics variants

Approximately 10 mL blood samples for DNA isolation will be collected from patients who have consented to participate in the genetic analysis component of the study.

3.4.2 Patient Global Impression of Change (PGIC) assessment

The PGIC will be captured weekly (± 2 days) from Week 1 to Week 4 (Visit 3) using the ePRO device.

The PGIC instrument is used for an overall evaluation of response to treatment. The patient will be asked to rate the degree of change in the overall asthma status compared to the first dosing (Week 0) using a 7-point scale, where 1 = much better; 2 = moderately better; 3 = a little better; 4 = about the same; 5 = a little worse; 6 = moderately worse; and 7 = much worse.

Patients will also be categorised according to the following three improvement categories at Week 1 to 4:

- Much better (1), moderately better (2), a little better (3) → A little better
- Much better (1), moderately better (2) → Moderately better
- Much better (1) → Much better

3.4.3 Eosinophil counts

Blood samples for determination of eosinophil count levels (haematology) will be taken at the time points detailed in the CSP and will be assessed in a central laboratory. Eosinophils will be presented in conventional units (cells/ μ L) in summaries.

3.4.4 Protein biomarkers

Whole blood for the preparation of serum for analysis of proteins and inflammatory markers will be collected at the screening visit (Visit 1) and at the visit to assess morning cortisol levels, according to Table 1 of the CSP.

3.4.5 Eosinophil-derived neurotoxin

Plasma samples will be collected according to the schedule in Table 1 of the CSP to evaluate EDN, a biomarker of eosinophil level and activation.

4. ANALYSIS METHODS

For analysis methods for the substudy, refer to the Addendum for the substudy.

4.1 General principles

The data analyses will be conducted using the SAS® System version 9.3 or above (SAS Institute Inc., Cary, NC). All SAS® programs used to generate analytical results will be developed and validated according to AstraZeneca SAS® programming standards.

For safety analyses, the statistical tabulation will be presented for all patients in the full analysis set (FAS). For demographics and patient characteristics and efficacy analyses, the

statistical tabulation will be presented for all patients in the FAS and for the following subpopulations:

- Patients with baseline OCS dose >10 mg/day, >5 mg/day to ≤10 mg/day, and 5 mg/day
- Patients with baseline blood eosinophil count:
 - <150/μL and ≥150/μL;
 - <300/μL and ≥300/μL;
 - <150, ≥150 to <300, and ≥300 cells/μL
- Patients with duration of chronic OCS use <1 year and ≥1 year.

For summary statistics for absolute and percentage OCS dose reduction from baseline to the end of the OCS reduction phase, the statistical tabulation will also be presented for the following subgroups:

- Patient's AI status at the end of the OCS reduction phase*:
 - Normal;
 - Partial AI;
 - Complete AI.

* Note that AI status at the end of the OCS reduction phase will be determined by the status at the repeat morning cortisol test (± ACTH stimulation test) for those with partial or complete AI at the initial morning cortisol test (± ACTH stimulation test) and by the status at the initial morning cortisol test (± ACTH stimulation test) for those with normal cortisol levels at the initial morning cortisol test (± ACTH stimulation test). Results from additional testing at the end of the OCS reduction phase for those with partial AI (see section 1.2) will not be included.

For summary statistics for absolute change in OCS dose from the end of the OCS reduction phase to the end of the maintenance phase, the statistical tabulation will also be presented for the following subgroups:

- Patient's AI status at the end of the maintenance phase:
 - Normal;
 - Partial AI;
 - Complete AI.

Continuous variables will be summarised using the mean, two-sided 95% CI of the mean, the standard deviation, median, minimum value, and maximum value. Categorical variables will be summarised using frequency counts and percentages, as well as a two-sided 95% CI for proportions computed using the exact Clopper-Pearson method. All patients in the corresponding analysis set will be considered the denominator. Time to event data will be summarised using median and 25th and 75th percentiles with 95% CIs. Data will be listed in patient level data listings.

No formal hypothesis will be tested in this study, and no multiplicity adjustment will be applied in the statistical analysis. No imputation will be performed beyond the approach defined for outcome measures in Section 4.2.6.3.

Due to the single-arm study design, external data sources may be used to contextualize any change seen in asthma control, asthma exacerbation rate, or other safety endpoints in patients treated with benralizumab following reduction of OCS. Any data sources identified, together with planned analyses, will be described in a separate analysis plan.

